Specific Aim 2: To evaluate the feasibility and preliminary effectiveness of a technology-delivered FBCO intervention for L/H families in rural Nebraska using RE-AIM and i-PARIHS. We will randomly assign participants to either the intervention or an enhanced standard care group (Figure 3). Sample Size Calculation. Sample size is based on the comparison of changes in BMI z-scores achieved by participants in FC-IVR with those achieved by participants in FC-workbook condition at 6 months post randomization²⁰. A total of 46 (23 per group) parent-child dyads achieves 80% power (alpha 0.05) to detect a significant difference between SC and IVR groups conditions. To account for a 25% attrition rate at 6-month we will recruit a total of 58 (29 per group) dyads. Participant Recruitment and Baseline Assessment Procedures. [name] will coordinate the recruitment of the participants with the help of CHWs. We will recruit a total of 58 dyads (Table 1). Baseline visits will take place at local community centers using private rooms. Dyads will complete informed consent, height, weight and waist circumference assessments, as well as complete a computer-based survey. Randomization will follow a random-numbers table (families/staff unblinded). Standard-Care. Families randomized to this group will receive FC-workbook. No additional materials or intervention contact will be provided. CHWs will follow a retention protocol to ensure these individuals return to 6-month assessments. Intervention Delivery. Families randomized to this group will receive the adapted version of the intervention described above. Drs. [name] and [name] will monitor IVR completion reports and assist the student-worker and CHWs in the on-going monitoring and engagement of participants during the intervention. Measurements and Data Collection. All measures (see table at PHS section for description) will be collected prior to intervention initiation and at 6 months post baseline (Figure 3). Weight will be assessed using a digital scale calibrated for accuracy prior to each assessment period using standard weights of a known quantity (e.g., 100-pound dumbbell). Height will be measured with a stadiometer, calibrated in 0.1-cm intervals. Waist circumference will be measured with a spring-loaded cloth tape measure at the level of the iliac crest using the average of the two closest measurements. Other Measures. Children and parents will complete measures of physical activity^{98,99}, eating behaviors¹⁰⁰, beverage intake¹⁰¹, quality of life^{102,103} acculturation^{104,105}, and health literacy¹⁰⁶. Parents will also complete home environment¹⁰⁷ surveys. During the 6-month assessment parents will complete program satisfaction surveys and a short exit interview with a CHW. Feasibility will be assessed according to intervention relevant factors (RE-AIM dimensions, engagement, attendance and completion rates), cost-effectiveness, cultural

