Maintenance	
 - Characteristics of completers vs non-completers - Intention to continue the intervention - Qualitative feedback on barriers/facilitators from participants/staff and leadership using i-PARIHS constructs 	
 -Demographic and clinical data from intake surveys [SW, CHWs] -Clinical data forms at 0,12 months [CHWs] -Qualitative interviews with participants, facilitators, staff, and health authorities [[name] , PI [name]] 	

Sample Size Calculation. Sample size is based on the comparison of changes in BMI z-scores achieved by participants in FC-IVR with those achieved by participants in FC-workbook condition at 6 and 12-month post randomization. A total of 46 (23 per group)

parent-child dyads achieves 80% power (alpha 0.05) to detect a significant difference between the FC-workbook and FC-IVR conditions, based on the relative BMI z-score differences (0.05) and standard deviation related to 6-month BMI z-score reduction for FC-IVR (0.06). To account for 25% attrition rate at 12-month, we will recruit a total of 58 (29 per group) parent-child dyads.

Cost Analysis: Costs will be assessed using time tracking spreadsheets and focused primarily on Aim 2 as it relates to the intervention delivery, though costs of participant recruitment will also be tracked using material and staff time to determine dollar amounts. [name] will complete A simple cost benefit analysis by assessing intervention implementation costs at 6-month post baseline by BMI z-scores reduction categories of unchanged, ≤ 0.1 , 0.1-0.25 and ≥ 0.25 , respectively.

Qualitative Analysis. Qualitative interviews will be recorded and transcribed in English or Spanish. The PI, with assistance from Drs. [name] and [name], will construct the interview codebook, with inductive codes added iteratively by in-depth reading of transcriptions until saturation is achieved. Transcripts will be double-coded in NVivo by [name]. Inter-coder reliability using Cohens kappa (goal > 0.80) will be assessed. The research team has extensive experience conducting qualitative investigation, possesses local linguistic expertise (Drs. [name] speak Spanish), and will be aided by community partners bilingual (English-Spanish) CHW staff.

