Statistical Analysis: Descriptive, parametric, and non-parametric statistical methods will be used to compare continuous and categorical variables among the intervention groups at baseline. Data will be examined for the presence of outliers, violations of normality (for those continuous variables) and missing data. Major violations of normality will be corrected with an appropriate transformation procedure or non-parametric methods . Multi-level mixed effect models will be employed to control errors of non-independence, heteroskedasticity caused by parent-child dyad heterogeneity, and potential covariates to control to detect the BMI z-score reduction differences between the two conditions. In its simplest form, the model generally can be shown as:

$$BMIZscore_{it} = \mu + \alpha_i + X_{ijt} \beta + W_i \sigma + TT_t + \theta d_i + T_t + v_{it}$$

All measures are obtained for 3 time periods: baseline, 6, and 12 months. The dependent variable is BMIZ score for participant i at time point t . The unobserved participant-level heterogeneity that is not time dependent is represented by α_i , is allowed to vary by parent-child-dyads and to be a random variable. The X_{it} are time-period-level covariates and the W_i are participant-level covariates. The model also contains treatment group indicators d_i , and

time period indicators T_t . Relative treatment effect between conditions will be captured by coefficient θ and is the variable of interest. Sensitivity analysis will be conducted to examine the robustness of the mixed effect model across different random-effect distribution specifications (e.g., normal, finite mixture of normal etc.). Additional outcomes (e.g., parent BMI, waist circumference, PA, sweet beverages intake and eating behaviors, acculturation, home environment changes and quality of life) will be analyzed using ANCOVA with the baseline measure as the covariate. If the ANCOVA assumptions are violated, a t-test (or if indicated, Wilcoxon's sum rank test) between group change scores (6 or 12 month measure and baseline measure) will be used. Significance level for all tests is 0.05. Analyses will be performed using R 3.6 (R Core Team).

F. Does this study involve the collection of blood, urine, saliva or other human biological material (HBM)?

No

DRUGS, BIOLOGIC DRUGS AND DEVICES

13. Drugs and Biologic Drugs

1. Does this research involve the use of drugs or biologics?

No

14. Devices

1. Does this research involve a medical device(s)?

No

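### The BMI z-score mixed model states no clear group-by-visit term and no within-child covariance; a random intercept alone could misstate the standard errors of visit-specific change effects, in either direction

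*Combined protocol and SAP*

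**What the plan says.** Section 12.E (Specific Aim 2, Statistical Analysis) plans multi-level mixed-effect models to detect differences between the two conditions in BMI z-score reduction. The equation is introduced with the words "In its simplest form, the model generally can be shown as". On timing, the section says: "All measures are obtained for 3 time periods: baseline, 6, and 12 months".

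The correlation between a child's repeated measurements comes from one term, α_i: "The unobserved participant-level heterogeneity that is not time dependent is represented by" it. The equation ends in v_it, which is never defined. No random slope, residual covariance structure or robust standard error is mentioned.

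On the estimand: "Relative treatment effect between conditions will be captured by coefficient" θ, which multiplies the group indicator d_i. No group-by-visit product is clearly displayed. The time indicator T_t appears twice in the equation as extracted, so such a product may have been garbled.

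The planned sensitivity analysis will "examine the robustness of the mixed effect model across different random-effect distribution specifications", with a normal and a finite mixture of normals as examples.

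The sample size text in the same section refers to changes in BMI z-score at 6 and 12 months. Section 12.B (Specific Aim 2) instead says that all measures "will be collected prior to intervention initiation and at 6 months post baseline", and its measures table has columns for those two visits only.

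**The concern.** A time-constant effect plus independent errors of constant variance is compound symmetry. Under that structure the 0-6, 6-12 and 0-12 month changes all have the same variance, namely twice the residual variance, and the model fits one averaged value to all three. The documents give no reason to expect equality. The 0-12 month interval is twice as long as the others. Section 12.B describes two classes and ten calls over 6 months, and no intervention contact for months 6 to 12.

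The sensitivity analysis would not reveal a problem, because it changes the shape of the distribution of α_i and not the covariance across visits.

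At stake is the calibration of the comparisons that section 12.E says it wants, namely differences in change. If the averaged variance is wrong for a given visit, the test there is either too liberal or too conservative, and the 6-month comparison, for which the only SD is given, may lose power.

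**Working it through.** **Plan's own figure.** Inputs from section 12.E, Sample Size Calculation: difference 0.05, SD of 6-month change 0.06, alpha 0.05 (taken as two-sided), power 80%.

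n per group = 2 × (1.960 + 0.842)² × (0.06/0.05)² = 22.6, rounded up to 23. The stated 23 per group reproduces. Power at 23 is 80.7% by the normal approximation and 78.9% by the noncentral t.

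**What the random-intercept model assumes.** Write V06, V6-12 and V0-12 for the true variances of the three changes. With complete data, independent errors and group-by-visit terms added, the model's variance for any change is

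m = (V06 + V6-12 + V0-12)/3.

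The ratio of model SE to true SE is √(m/V06) at 6 months and √(m/V0-12) at 12 months. A nominal 5% test then has actual size 2 × [1 − Φ(1.96 × ratio)].

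**Inputs not in the documents.** Only V06 = 0.06² = 0.0036 is given. No 12-month SD, 6-12 month SD or between-visit correlation is stated. The rows below assume V6-12 = V06 and vary V0-12.

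| V0-12 / V06 | SE ratio, 6 m | SE ratio, 12 m | Type I, 6 m | Type I, 12 m |
|---|---|---|---|---|
| 0.8 | 0.97 | 1.08 | 5.8% | 3.4% |
| 1.0 | 1.00 | 1.00 | 5.0% | 5.0% |
| 1.25 | 1.04 | 0.93 | 4.1% | 6.8% |
| 1.5 | 1.08 | 0.88 | 3.4% | 8.4% |
| 2.0 | 1.15 | 0.82 | 2.4% | 11.0% |

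Worked example, ratio 2: m = 0.0036 × (1 + 1 + 2)/3 = 0.0048. Model SE = √(0.0048 × 2/23) = 0.0204. True SE is √(0.0036 × 2/23) = 0.0177 at 6 months and √(0.0072 × 2/23) = 0.0250 at 12 months. In simulation the 12-month type I error for this case was 10.6% (23 per group) and 10.9% (29 per group).

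**6-month power.** For ratio 2, 0.05/0.0177 = 2.83 and the effective critical value is 1.96 × 1.155 = 2.26, so power = Φ(2.83 − 2.26), about 71%, against 80.7% with the correct SE. Simulation gave 69.6%, against 78.9% by the noncentral t.

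**Pooled post-baseline effect.** The model variance is 0.75m. The true variance is (V06 + V0-12 + 2C)/4, with C = (V06 + V0-12 − V6-12)/2. In units of V06:

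- Ratio 1.25: 0.8125 against 0.875, type I error 5.9%.
- Ratio 1.5: 0.875 against 1.0, type I error 6.7%.
- Ratio 2: 1.0 against 1.25, type I error 8.0%.

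**A pattern with both intervals too narrow.** Let V6-12 = 0.3 × V06 and V0-12 = 1.2 × V06. Then m = (1 + 0.3 + 1.2)/3 = 0.833 × V06. The SE ratios are 0.91 and 0.83, and type I error is 7.4% at 6 months and 10.2% at 12 months.

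**θ taken literally.** As a group main effect with complete data, θ is a difference between group averages of child-level means, and its variance is estimated directly from the spread between children. Simulation (29 per group, assumed baseline SD 0.3 or 0.5, V0-12/V06 of 2 or 3.9, 0% or 25% dropout, 1,500 runs each) gave SE ratios of 0.97 to 1.03 and rejection rates of 4.4% to 6.2%.

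**The case against.** Four objections carry weight.

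First, the equation as displayed yields one coefficient, θ, on the group indicator. It produces no 6-month or 12-month treatment effect, so it has no visit-specific intervals to be wrong, and the SE of θ itself is sound. This stands. The point therefore bears only on change effects. Those are nevertheless what the surrounding text asks for: section 12.E speaks of differences in reduction, and the sample size text of changes at 6 and 12 months.

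Second, a reader might infer that the intervals are definitely too wide at 6 months and too narrow at 12. The documents do not support that. It requires change variance to grow with time, and the only SD given is for 6 months. A doubled variance already corresponds to uncorrelated successive changes. A fourfold variance (12-month type I error 16.6% by the formula) needs perfectly correlated ones, which is the mathematical extreme for these inputs.

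Third, it is too strong to say that the plan commits itself to compound symmetry. The equation is offered as the simplest form, v_it is undefined, and the displayed terms may be damaged. Likewise, the heteroskedasticity that the section says it controls is attributed to differences between dyads, so the text does not promise to handle variance that changes over time.

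Fourth, section 12.B lists only baseline and 6 months and names a chi-square test on a proportion for the primary outcome. With two visits there is a single between-visit change and nothing to average. This also stands, but section 12.E and the compensation text in section 23 both refer to a 12-month visit, so the documents leave it unresolved.

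**Conclusion.** The concern holds as a gap in specification with a conditional consequence. Section 12.E states neither a clear group-by-visit term nor a within-child covariance. If visit-specific or pooled change effects are estimated with a random intercept and independent errors, their standard errors may be wrong in either direction.

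For V6-12 = V06, 12-month type I error runs from about 5% (0-12 month variance equal to the 0-6 month variance) through 6-7% (1.25 times) and 8-9% (1.5 times) to 10-11% (twice), with the 6-month test increasingly conservative. These figures rest on complete data, 23 per group for the standard errors and power, and assumed variance ratios that the documents do not supply. They do not apply to θ as a literal main effect, nor to an analysis of baseline and 6 months alone.

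**What to change.** In section 12.E, Statistical Analysis:

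- Write the BMI z-score model with group-by-visit terms, and define the treatment effect as the between-group difference in change from baseline at 6 months and at 12 months.
- Use an unstructured within-child covariance over the three visits, with Kenward-Roger or Satterthwaite degrees of freedom.
- Keep the random-intercept fit as a sensitivity analysis.
- State whether the 12-month visit is part of this analysis, so that sections 12.B and 12.E agree.

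Both changes to the model are needed. With an unstructured covariance but no group-by-visit term, θ would still average in baseline, and if changes accumulate independently over time nearly all its weight would fall on the baseline visit.

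The cost is SAP wording and a few lines of R. An unstructured 3 × 3 covariance has six parameters against two for the random intercept, so four more are estimated from about 46 to 58 children. The specification remains valid whichever way the change variances run, and fixing it before analysis removes a data-driven choice.

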Effectiveness	
 -Primary outcome (BMI z-score) and secondary clinical and self-management outcomes (Table 2) by control/IVR -Comparison of outcomes in subjects who withdraw vs. complete intervention - Staff and leaderships perceptions about delivering FBCO program via IVR and group sessions 	
 -Recruitment/enrollment/subject tracking logs (including completion, dropout and loss to follow-up rates/reasons) [CHWs] -Clinical data forms and surveys at 0,6 months [SW, CHWs] -Qualitative interviews with staff and leadership [[name] , PI [name]] 	
 Selected constructs will include: Facilitation: IVR and group based sessions and workbook facilitation strategies; Innovation: adaptation to deliver strategies to L/Hs in the context of rural NE
Adoption	
 - Staff and leaderships perceptions about delivering FBCO program via IVR and group sessions 	
 -Qualitative interviews with staff and leadership [[name] , PI [name]] 	Recipients : perceptions of participants (Beneficiaries), and staff (Recipients)
Implementation	
 - IVR completion reports; group session attendance and observation reports; proportion of content delivered as intended (fidelity) - Changes made during the implementation process (adaptation) tracked by the FRAME - Number of Calls completed and contact hours - Participant satisfaction - Qualitative feedback on barriers/facilitators from L/Hs/staff using i-PARIHS constructs 	
 -IVR completion forms (IVR System) [[name]] -IVR logged call duration (IVR System) [[name]] - Participant Satisfaction survey [SW, CHWs] -Qualitative interviews with participants, staff [[name] , PI [name]] 	Context : documentation of the capacity (human and financial resources); assessment of support from the leadership at the state and local levels

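### The mixed model's single treatment coefficient θ is tied to no visit, although the plan mainly places effectiveness at 6 months

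*Combined protocol and SAP*

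**What the plan says.** Section 12.E, Statistical Analysis, specifies a multi-level mixed model with a participant random term, covariates, a treatment indicator d_i and time-period indicators T_t. On timing it states: "All measures are obtained for 3 time periods: baseline, 6, and 12 months". On the estimand it states: "Relative treatment effect between conditions will be captured by coefficient θ and is the variable of interest". No sentence ties θ to 6 months, to 12 months or to an average, and the prose describes no group-by-time term.

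Other parts of the plan do attach visits:

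- Table 1 (section 12.E), Effectiveness row, lists "Primary outcome (BMI z-score) and secondary clinical and self-management outcomes (Table 2) by control/IVR", with "Clinical data forms and surveys at 0,6 months" as a data source. The Maintenance row lists "Clinical data forms at 0,12 months".
- The Aim 2 hypothesis (section 2) concerns 6 months, as does the sizing comparison in sections 4 and 12.B.
- The sizing in section 12.E uses a difference of 0.05 and the "standard deviation related to 6-month BMI z-score reduction for FC-IVR (0.06"). The same paragraph words the comparison with "those achieved by participants in FC-workbook condition at 6 and 12-month post randomization" and continues "To account for 25% attrition rate at 12-month".
- On whether 12 months is measured at all, section 12.E and section 23 (Compensation) include that visit. The measurement paragraph of section 12.B and the study-measures table list only baseline and 6 months.

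**The concern.** A model with three visits and one treatment coefficient has to combine visits in some way, and the combination determines what θ estimates. Table 1 separates effectiveness (0 and 6 months) from maintenance (0 and 12 months), but the model does not carry that split over. If the effect changes after the 6-month program, a combined θ no longer estimates the 6-month effect, and its power can differ markedly from what the 6-month inputs imply. Leaving the contrast unnamed also allows it to be settled after the data are seen.

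**Working it through.** **Inputs from the plan.** Difference 0.05; SD of 6-month change 0.06; alpha 0.05 (two-sided assumed, sidedness not stated); 80% power; 23 per arm evaluable, 29 per arm recruited.

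**Assumed, because the plan does not give them.** Share of the effect left at 12 months: 100%, 50% or 0%. Between-child SD of BMI z-score (σb): 0.1 to 0.6. Random intercept with independent residuals, so the residual variance is 0.06²/2 = 0.0018.

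**1. The plan's own figure.** n per arm = 2 × (1.96 + 0.84)² × 0.06² / 0.05² = 22.6, so 23 per arm and 46 in total. This reproduces section 12.E. The inputs describe a comparison of 6-month changes. Power at 23 per arm is 80.7% (normal) or 78.9% (noncentral t).

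**2. θ as printed (θ d_i + T_t, a main effect).** With balanced visits and no baseline difference, the expected θ is (0 + 0.05 + e12)/3, where e12 is the 12-month difference:
- e12 = 0: 0.017
- e12 = 0.025: 0.025
- e12 = 0.05: 0.033

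That is one third to two thirds of 0.05. With baseline and 6 months only, it would be (0 + 0.05)/2 = 0.025.

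**3. θ as one group-by-post-baseline product.** With both visits complete, the expected θ is (0.05 + e12)/2, that is 0.05, 0.0375 or 0.025 at 100%, 50% or 0% remaining. If only baseline and 6 months are collected, θ is exactly the 6-month contrast and the problem disappears.

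**4. Power at 23 per arm, free baseline group term (normal approximation).**
- Averaged θ: SE = √(2 × 0.0018 × 1.5 / 23) = 0.01532. The ratios 0.05, 0.0375 and 0.025 over 0.01532 are 3.26, 2.45 and 1.63, giving power 0.904, 0.687 and 0.371.
- 6-month contrast: SE = √(2 × 0.0036 / 23) = 0.01769. The ratio is 2.83, giving power 0.807.

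**5. The same with a common baseline mean.** The variance per child given baseline is σb² + 0.0018/k − σb⁴/(σb² + 0.0018), with k = 2 for the average and k = 1 for 6 months alone.

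| Effect remaining at 12 months | Averaged θ, σb 0.1 to 0.6 | 6-month contrast |
|---|---|---|
| 100% | 0.931 to 0.905 | 0.837 to 0.808 |
| 50% | 0.733 to 0.688 | same |
| 0% | 0.406 to 0.372 | same |

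**6. Small-sample check.** Simulation with t-tests gave 0.90, 0.66 and 0.33 for the averaged θ and 0.78–0.80 for the 6-month contrast, slightly lower than the table.

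**7. Break-even.** Averaging loses power when (1 + share)/2 falls below the ratio of the two SEs. With a free baseline the ratio is √(0.0054/0.0072) = 0.866, so the share is 0.73. With a common baseline and σb 0.1 it is 0.71. If the 6- and 12-month change scores correlate at 0.7–0.8 rather than the 0.5 implied here, the ratio √((1 + ρ)/2) is 0.92–0.95 and the break-even share rises to about 84–90%.

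**8. Cost of naming 6 months under full persistence.** With 23 complete per arm: 0.904 − 0.807 = 0.097. With 29 per arm and 25% missing only at 12 months (common baseline): 0.962 − 0.910 = 0.052. With 29 per arm and the same 25% missing at both visits: 0.917 − 0.816 = 0.101. This is about 5–10 points.

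**The case against.** The strongest reply is that the equation is damaged. It prints a time term twice, which suggests a lost product of d_i and T_t. T_t is described as a set of indicators, so θ could stand for visit-specific effects and the model might already be adequate. This cannot be excluded from the text available. It does not close the point, because the prose speaks of one coefficient and, even with several, does not say which visit is of interest.

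Other parts of the reply also stand:

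- The 12-month visit is disputed within the plan. Under the product reading, everything here depends on it.
- Section 12.E words the sizing as 6 and 12 months and takes attrition at 12 months, so an average may be intended. But no 12-month effect or SD is given.
- The Maintenance row lists 12-month forms as a data source, but BMI z-score is not among its measures. Calling a 12-month coefficient the maintenance estimate goes a little beyond the table.
- The chi-square test of the proportion reducing BMI z-score (section 12.B), which that section calls primary, is unaffected.

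Two stronger inferences are tempting. A reader might take the printed main effect at face value and conclude that the trial has almost no power. With an assumed between-child SD of 0.2–0.6, that reading gives about 5–9% at 23 per arm. The documents do not support quoting this as the trial's power, since it rests on a damaged equation and an undocumented SD. A reader might also infer that averaging necessarily weakens the trial. It does not: above the break-even share it gains power. The relapse-prevention content of calls 7–10 (section 12.B) gives some ground for expecting persistence, though no figure.

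**Conclusion.** The point holds as an undefined contrast that should be fixed before analysis, with medium confidence. As printed, θ is a main effect diluted by baseline to about one third to two thirds of the 6-month effect. Read as a single product, it is a 6- and 12-month average. Neither reading is tied to the 6-month contrast that Table 1, the Aim 2 hypothesis and the 0.06 SD point to. The plan's own reference to 6 and 12 months in the sizing adds to the ambiguity.

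Under the product reading, the illustrated power at 23 complete dyads per arm runs from about 90–93% down to 37–41%, against 81–84% for the 6-month contrast. These figures depend on assumed persistence, between-child SD, a random intercept and independent residuals. The share of the effect that persists sets even the direction of the difference, so they are not a forecast.

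**What to change.** First check the equation against the source file, and reconcile the visit schedule (section 12.B and the study-measures table against sections 12.E and 23). Then keep the model and covariates, but write treatment as group-by-visit terms:

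`BMIz_it = μ + α_i + X_it β + W_i σ + τ6·I(t=6) + τ12·I(t=12) + γ·d_i + θ6·d_i·I(t=6) + θ12·d_i·I(t=12) + v_it`

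Either keep γ free or set it to zero for a common baseline, and say which. Name θ6 as the effect of interest. Report θ12 with its interval as supportive, or drop the 12-month terms if that visit is not collected. If the sponsor wants the 6- and 12-month average, section 12.E should say so and the sizing should state a 12-month effect.

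Naming θ6 takes about two sentences once the schedule is settled, with no change to data collection or sample size. Its statistical cost is the 5–10 points of power given up relative to averaging if the effect fully persists.

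### The fallback for secondary outcomes drops the baseline covariate and, for skewed outcomes with weak to moderate baseline correlation, loses power that a baseline-adjusted fallback would keep

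*Combined protocol and SAP*

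**What the plan says.** Section 12.E (Statistical Analysis, Specific Aim 2) names the outcomes concerned: "Additional outcomes (e.g., parent BMI, waist circumference, PA, sweet beverages intake and eating behaviors, acculturation, home environment changes and quality of life". They "will be analyzed using ANCOVA with the baseline measure as the covariate". The fallback follows: "If the ANCOVA assumptions are violated, a t-test (or if indicated, Wilcoxon's sum rank test) between group change scores", the change being from baseline to 6 or 12 months. Section 12.B (Specific Aim 2, Statistical Analysis) has the same rule, opening with the same words ("If the ANCOVA assumptions are violated, a t-test"), for the 6-month change.

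Neither section says which ANCOVA assumptions are checked, by what means, or what makes the Wilcoxon test the indicated one.

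Section 12.E has a general provision earlier in the same paragraph: "Major violations of normality will be corrected with an appropriate transformation procedure or non-parametric methods". It does not say whether this comes before the change-score fallback, or whether the non-parametric methods it has in mind are the Wilcoxon test on change. The statistical paragraph in 12.B has no transformation step. It does allow medians and inter-quartile ranges as summaries, so departures from normality are expected.

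**The concern.** The outcome table in 12.B includes servings of fruit and vegetables, sugar-sweetened drinks, time in exercise and number of healthy days. These are self-reported quantities that are plausibly skewed, with only moderate correlation between baseline and follow-up. They are therefore the likeliest to fail a normality check and be moved to the fallback.

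For skew, that move has two weaknesses:

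- The t-test on change still works on the raw skewed scale, so it does not address the skew.
- Both change-score tests subtract the whole baseline value instead of estimating how much of it carries over. This fixes the baseline slope at 1. When the true slope is well below 1, subtraction adds noise.

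At stake is the chance of seeing a real difference in the behavioural outcomes of a trial planned around 23 evaluable dyads per arm. A second issue is that the method may differ from outcome to outcome on a trigger that is not written down.

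**Working it through.** **1. The plan's sample size, to fix n.** Section 12.E says that 46 (23 per group) "parent-child dyads achieves 80% power (alpha 0.05"), "based on the relative BMI z-score differences (0.05) and standard deviation related to 6-month BMI z-score reduction for FC-IVR (0.06"). Taking alpha as two-sided, n per arm = 2 × (1.960 + 0.842)² × (0.06/0.05)² = 2 × 7.849 × 1.44 = 22.6, so 23. The figure reproduces. It concerns BMI z-score only; no power is stated for the secondary outcomes. The steps below use 23 per arm unless noted, and alpha 0.05 as planned ("Significance level for all tests is 0.05").

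**2. Normal outcomes, equal SDs at both visits.** With baseline–follow-up correlation ρ, the variance of the group difference is proportional to 1 − ρ² for ANCOVA and 2(1 − ρ) for the change score. The ratio is 2/(1 + ρ). If the effect gives ANCOVA 80% power, the change-score t-test has power Φ(2.802 × √((1 + ρ)/2) − 1.960).

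| ρ (assumed) | Variance ratio | Power, t-test on change |
|---|---|---|
| 0.3 | 1.54 | 62% |
| 0.5 | 1.33 | 68% |
| 0.7 | 1.18 | 73% |
| 0.85 | 1.08 | 77% |
| 0.9 | 1.05 | 78% |

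The ratio depends on equal SDs. In a simulated case with a true baseline slope of 1 and correlation 0.7, the change-score test had 79% power against 78% for ANCOVA, so nothing was lost.

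**3. Skewed outcomes (simulation).** Assumptions: log-normal, log SD 0.8 (skewness about 3.7), ρ = 0.5 on the log scale, and a shift of 0.8 SD on the log scale. That is 0.8 × 0.8 = 0.64 log units.

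| Method | Outcome lowered | Outcome raised |
|---|---|---|
| Rank ANCOVA | 83% | 83% |
| Wilcoxon on change | 54% | 75% |
| t-test on change | 43% | 67% |

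Rank ANCOVA gains 83 − 54 = 29 points over Wilcoxon when the outcome falls and 83 − 75 = 8 when it rises. Over the t-test it gains 83 − 43 = 40 and 83 − 67 = 16. Direction matters for this trial: 12.B aims to raise activity and fruit and vegetable intake, and to lower sugary drinks and screen time.

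**4. Wider range.** Here the effect was set so that ANCOVA on the log scale had about 80% power, with log SD 0.5 to 1.0 and ρ 0.3 to 0.85 (10,000 trials per setting). At log SD 0.8 and ρ 0.5 the change-score tests had 39% and 49%, close to the lowered-outcome column above, so these ranges are the unfavourable end.

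| Method | Power |
|---|---|
| t-test on change | 29–62% |
| Wilcoxon on change | 40–66% |
| Raw-scale ANCOVA | 53–74% |
| Rank ANCOVA | 72–77% |
| Log-scale ANCOVA | 79–80% |

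**5. Is raw-scale ANCOVA with robust (HC3) errors enough?** No. In the step 3 setting with 22 per arm:

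- Outcome lowered: HC3 63%, Wilcoxon on change 53%.
- Outcome raised: HC3 68%, Wilcoxon on change 74%.
- Outcome raised, ρ = 0.7: HC3 76%, Wilcoxon on change 89%.

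**6. Type I error.** Under skew, both change-score tests stayed at 3.9–5.2%. With unequal slopes (0.8 and 0.2) the t-test was at 5.0–5.2% and Welch at 4.8–4.9%. Wilcoxon was at 5.4%, rising to 6.4% with strongly unequal variances. Each test was checked by itself, not the rule that chooses between them.

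**The case against.** Much can be said for the plan.

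- **Transformation is already allowed.** Section 12.E provides for it, and transforming before ANCOVA would avoid most of the loss. This stands as far as it goes. But the order of steps is not given, the non-parametric alternative may simply be Wilcoxon on change, and 12.B lacks the provision.
- **Wilcoxon is the natural choice for skewed data.** The t-test figures are then probably not what the plan would produce for those outcomes. This stands, so the Wilcoxon column is the fairer comparison. Its deficit is 29 points in one direction and only 8 in the other.
- **Change scores do help with some violations.** They need neither linearity nor parallel slopes, and Wilcoxon does not need normality. A reader might infer that the fallback cures nothing; step 6 does not support that.
- **Change scores are not always less precise.** A reader might infer a loss whenever the correlation is below 1. That needs equal SDs, and step 2 shows a case with no loss.
- **The target does not change for the t-test.** Under randomisation, ANCOVA and the t-test on change estimate the same mean difference. Only Wilcoxon asks a different question.
- **These are secondary outcomes of a feasibility trial, with no stated power.** This stands and limits the weight of the point.

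**Conclusion.** The point holds as one of efficiency and pre-specification. When ANCOVA assumptions fail, both sections move to tests that discard the baseline covariate, although methods that keep it are available and perform better under skew. Under the assumptions of step 3, the shortfall against rank ANCOVA is 8 to 29 points for Wilcoxon and 16 to 40 for the t-test, depending on the direction of effect. For near-normal outcomes with high baseline correlation it is 2 to 3 points (77–78% against 80% at ρ 0.85 to 0.9).

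The skewness, correlations and effect sizes are assumed, because the documents give none. The ranking of methods matters more than the levels.

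A reader might infer that the fallback makes the secondary results invalid, or that real effects will be missed. Neither is supported: error rates are held, and whether the fallback would be triggered is plausible but not stated. The analysis of BMI z-score is not affected.

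**What to change.** In both 12.B and 12.E, replace the change-score fallback with a baseline-adjusted one and state the order:

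1. ANCOVA on a transformed scale where the outcome permits, with baseline transformed in the same way. For servings, drinks and activity time, name a transformation that handles zeros.
2. Otherwise rank ANCOVA: ranked follow-up on ranked baseline, with group.

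Assign the method to each outcome in advance where possible. Where a check on the data must decide, state the check and its threshold. Tie the general transformation provision in 12.E to this sequence, and give 12.B the same wording. Do not rely on raw-scale ANCOVA with HC3 errors as the remedy for skew.

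The cost is a few sentences in two places. No new data are needed, and the R software named in 12.E suffices. One small downside is that rank ANCOVA gives no effect in natural units, so report an unadjusted or raw-scale difference beside it.
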